1.4 Research Hypothesis

Intravenous Tranexemic acid given preoperatively at 15mg/kg before open femoral shaft fracture intramedullary nailing will reduce average perioperative blood loss of 3.31 g/dl and perioperative transfusion rates by 30%.

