3.1 Study design

This will be an open label single arm trial involving adult patients undergoing open intramedullary femoral shaft nail fixation at Mulago National Referral Hospital.

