3.6 Sample size estimation

3.6.1 Sampling Procedure

Comparison of Two Means (Minn M. Soe and Kevin M. Sullivan, Emory University)

$$n = \frac{(Z_1 + Z_2)^2}{(u_1 - u_2)^2} 2(S)^2$$

$$(u_1 - u_2)^2$$

n = Sample size in each group

Z₁ = 1.96 for 95% confidence level

Z₂ = 0.84 for 80% power

S = Standard Deviation of Outcome in Control Group

u₂ - u₁ = minimum meaningful difference between means

In study done in Mulago by Kajja et al estimated blood loss in 93 patient who underwent open femur shaft fracture intramedullary nailing estimated 72 hours postoperative mean total blood loss at 3.31g/dl, (SD 1.56).

Tranexemic Acid is expected to give 30% reduction in Blood Loss

i.e. $u_1 - u_2 = 0.3$

u₁

$$\underline{3.31 - u_2} = 0.3$$

3.31

$$u_1 - u_2 = 0.993$$

$$n = (1.96 + 0.84)^2 2 \times 1.56^2$$

$$0.993^2$$

$$= 38.7$$

[figure not shown]
$$n = 39$$

$$\text{Adjust for non-response} = 39 / 0.9$$

$$= 43.3 = 43$$

$$N = 43$$

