3.12 Statistical analysis

Data will then be exported into a SPSS version 19 system which will be used for analysis. We will summarise the study population. We will use descriptive statistics such as means (standard deviations) or median and interquartile range (IQR) for continuous variables and proportions for categorized variables. We will also conduct appropriate statistical tests such as chi square or Fischer's test for categorical variables and a one sample independent T-test or wilcoxon sum rank test for continuous variables.

Objective 1: *To determine the effectiveness of pre-operative intravenous Tranexemic acid 15mg/kg on reduction of perioperative blood loss as estimated by difference in 72 hour postoperative and 2 hour preoperative Hemoglobin concentration in patients undergoing open intramedullary nailfixation offemoral shaftfractures in Mulago National Referral Hospital.*

We will assess for the hypothesis that TXA reduces perioperative blood loss by at least 30% using one sample independent T-test

Objective 2: *To determine effectiveness of pre-operative intravenous Tranexemic acid 15mg/kg on reduction of transfusion rates by 30% inpatients undergoing open intramedullary nail fixation offemoral shaftfractures in Mulago National Referral Hospital.*

We will conduct univariate analysis and adjust for effect modification and confounding.

Objective 3: *To determine the safety of pre-operative intravenous Tranexemic acid 15mg/kg in patients undergoing open intramedullary nailfixation offemoral shaftfractures in Mulago National Referral Hospital.*

We will assess for safety using descriptive statistics showing proportions of adverse events in the study group.

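### The one-sample t-test for blood loss treats a 93-patient historical mean as error-free, so the two-sided type I error at a nominal 5% is about 10% if the test value is 3.31 g/dl, or 7.3-7.6% if it is 70% of 3.31

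*Combined protocol and SAP*

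**What the plan says.** Section 3.1 sets the design: "This will be an open label single arm trial involving adult patients undergoing open intramedullary femoral shaft nail fixation". There is no concurrent control.

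The comparator comes from section 3.6.1, which cites an earlier series at the same hospital: "93 patient who underwent open femur shaft fracture intramedullary nailing estimated 72 hours postoperative mean total blood loss at 3.31g/dl, (SD 1.56"). Section 1.4 builds the hypothesis on the same number; tranexamic acid "will reduce average perioperative blood loss of 3.31 g/dl", with 30% as the target.

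Section 3.12, Objective 1, names the analysis: "We will assess for the hypothesis that TXA reduces perioperative blood loss by at least 30% using one sample independent T-test". It gives no test value, no final alpha and no sidedness, plans no confidence interval, and makes no allowance for the historical mean being an estimate. The only pointer to alpha is in the sample-size section: "Z₁ = 1.96 for 95% confidence level", which implies 5% two-sided.

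The sample size itself uses a formula for two independent means, with the factor 2 for two variances and n defined per group.

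**The concern.** A one-sample t-test compares the trial mean with a constant. Here the constant is a sample mean from 93 patients, or a multiple of it. Its sampling error is about two thirds as large as that of the trial mean, so leaving it out understates the standard error of the comparison. The test then rejects too often, and any interval reported beside it is too short.

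This would be so even if the historical patients were perfectly comparable with the trial patients, so it is separate from the question of comparability. It affects the primary p-value, and section 1.3 intends the findings to feed hospital and Ministry of Health protocols. The planned test is also out of step with the sample size, which does allow for comparator variance.

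**Working it through.** **Inputs.** Historical mean 3.31 g/dl, SD 1.56, n = 93; planned difference 0.3 x 3.31 = 0.993 g/dl; z values 1.96 and 0.84; 39 evaluable patients, 43 enrolled (all section 3.6.1). Assumed: SD 1.56 in the trial as well, a comparable cohort, a two-sided 5% test and no interim looks.

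**The plan's own figure.** n = (1.96 + 0.84)² x 2 x 1.56² / 0.993² = 38.7, so 39; 39/0.9 = 43.3, written as 43. This reproduces. Without the factor 2 the formula gives 19.3, so the sizing clearly counts a second variance.

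**Standard errors.**
- Historical mean: 1.56/√93 = 0.162 g/dl (95% CI for 3.31: 2.99 to 3.63).
- Trial mean: 1.56/√39 = 0.250; 1.56/√43 = 0.238.
- Difference: 1.56 x √(1/n + 1/93) = 0.298 at n = 39 and 0.288 at n = 43.
- Ratio of the correct to the planned standard error: √(1 + n/93) = 1.191 and 1.209.

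**Type I error, test value 3.31.** With equal SDs the one-sample statistic is a t variable multiplied by that ratio r, so the two-sided error is 2 x P(t with n − 1 df > c/r), where c is the usual critical value.
- n = 39: c/r = 2.024/1.191 = 1.699, giving 9.7%.
- n = 43: c/r = 2.018/1.209 = 1.669, giving 10.3%.

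Simulation agrees (9.7-9.8% and 10.2-10.3%). The tail favouring tranexamic acid is 4.9% and 5.1%, against 2.5% intended. A Welch test from the summary data holds 5.0% in the same simulations.

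**Type I error, test value 0.7 x 3.31 = 2.317.** The historical error is scaled by 0.7, so r = √(1 + 0.49n/93) = 1.098 (n = 39) and 1.108 (n = 43). The error is 7.3% and 7.6%. Here the null is a true reduction of exactly 30%, not an absence of effect.

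**Interval.** Half-width for the difference (z = 1.96): 0.49 instead of 0.58 g/dl at n = 39, and 0.47 instead of 0.56 at n = 43. That is 16-17% too narrow, with true coverage of about 90%.

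**Where the two tests disagree.** At n = 39 with an observed SD of 1.56, the smallest significant difference from 3.31 is 2.024 x 0.250 = 0.506 g/dl (15.3%) for the one-sample test and 1.994 x 0.298 = 0.593 g/dl (17.9%) for Welch.

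**Power at 0.993 g/dl, historical error included for both tests.**
- One-sample: Φ((0.993 − 0.506)/0.298) = 95% at n = 39; 96% at n = 43.
- Welch: Φ((0.993 − 0.593)/0.298) = 91% at n = 39; 93% at n = 43.

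The 98-99% obtained when 3.31 is taken as exact (normal approximation) is not a like-for-like figure.

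**The case against.** The best defence is that comparison with a fixed benchmark is an accepted single-arm analysis. If 3.31 were a performance target, the one-sample test would hold its 5%, and the 10% is an average over repeats of a cohort already observed. That would be a good answer for a chosen target. But the protocol presents 3.31 as an estimate of usual blood loss in one cohort, asks whether the drug lowers that loss, and sizes the trial with two variances. The defence does not carry.

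Other objections stand in part:

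- **The test value is unstated.** A reader might infer an unconditional false-positive rate of 10%. The documents do not support that. Read literally, a test of at least a 30% reduction has a null of 2.317, and the error is then 7.3-7.6%. The 3.31 reading fits the sizing better, because a null placed at the planned effect would leave no power for that effect, but it remains an inference.
- **Direction.** A reader might infer an error that only favours the drug. It does not; both tails are inflated, and about half of the 10% is false evidence of harm.
- **Confidence interval.** None is planned, so the narrowness applies only to an interval that might accompany the test.
- **Wording.** One sample and independent contradict each other as names for a t-test, and the data collection sheet still has Study Arm A and B. The single-arm design supports the one-sample reading.
- **Practical effect.** At n = 39 the tests disagree only for observed reductions of about 15-18%, well below the 30% sought. This bears on severity, not on whether the test is right.

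**Conclusion.** The planned primary test is wrong as written, because it gives no variance to a comparator that is itself an estimate from 93 patients. At a nominal two-sided 5%, the type I error is about 10% if the null is 3.31 (9.7% at n = 39, 10.3% at n = 43) and 7.3-7.6% if it is 0.7 x 3.31. Against 3.31, false claims of benefit rise from 2.5% to about 5%.

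These figures assume SD 1.56 in both groups and a comparable cohort, and leave out the two interim looks. A smaller SD in the trial would make the inflation worse; a larger one would reduce it. They describe sampling error only. A reader might infer that a corrected test makes the historical comparison sound, but it does not. Section 3.2, for instance, says that intravenous tranexamic acid is already sometimes used at the site, and no choice of test removes bias of that kind.

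This should be fixed, but it does not threaten the trial's feasibility.

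**What to change.** In section 3.12, Objective 1:

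1. State the null value, alpha and sidedness.
2. Replace the one-sample test with a Welch two-sample comparison from summary data: trial mean, SD and n against 3.31, 1.56 and 93.
3. Report the difference and the percent reduction, 1 − (trial mean/3.31), with a 95% CI that carries the historical standard error (delta method or Fieller).
4. Judge any 30% criterion by that interval and not by a fixed cut-off. For illustration, a trial mean of 2.317 with n = 39 has a delta-method standard error of √(0.250² + 0.49 x 0.162²)/3.31 = 0.083, so an observed 30% reduction would have an interval of about 14% to 46%.
5. Say that the analysis allows for sampling error in the historical mean but not for non-comparability of the cohort.

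The cost is one paragraph and no new patients or data. Power at 0.993 g/dl falls from about 95-96% to about 91-93%, still above the stated 80%.

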2.3 Tranexemic Acid in orthopaedic surgery

2.3.1 Tranexemic acid in spine surgeries

Both intravenous and topical Tranexemic acid have been employed in spine surgery. Meta-analysis data analysis showed TXA reduced intraoperative, postoperative, and total blood loss by averages of 219, 119 (-141, - 98; p<00001), and 319 mL, respectively. 33% reductions in blood transfusion (0.54, 0.83; p<000001) and no apparent increase in Deep Venous Thrombosis (DVT) nor myocardial infarctions.(27)

Pradeep et al used intravenous TXA 10mg/kg versus placebo preoperatively in stabilization surgeries noted a significant decrease in intraoperative blood loss 1042ml in cases and 1149 in controls (p<0.033), thereby decreasing intraoperative transfusions however they noted that there was no major impact on postoperative blood loss 318ml in cases and 354 in controls. In their study they did not observe any thromboembolic events nor adverse effects.(15)

Ho Yong Choi et al also used intravenous loading dose ofTXA 10mg/kg in spinal deformity correction and noted use ofTXA can provide beneficial effects not only on reducing surgical bleeding (case 841 vs. controls 1336 mL, p=0.002), but also on decreasing transfusion requirements both intra- and postoperatively (cases 544 vs. control 812 mL, p=0.012; cases 193 vs. control 359 mL, p=0.034). They further noted no difference in the Incidence of

thromboembolic event and other complications did not show any differences between TXA and non-TXA groups.(28)

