2.3.2 Tranexemic acid in Arthroplasty

In orthopaedics, TXA use has been explored most in field of hip and knee arthroplasty with both topical and intravenous routes of administration used however the most common route remains intravenous. However Topical administration ofTXA at an intra-articular and/or peri-articular soft tissue level is growing in popularity. With one of the advantages of topical use of TXA is the minimal systemic absorption hypothesizing less systemic adverse effects.(23, 29)

In hemi and total hip arthroplasty, most randomized placebo controlled trials clinical trial found that TXA administration safely reduced blood loss (TXA group was 242 mL lower on Postoperative Day (POD) 1 (731 vs. 973 mL, P = 0.01), 294 mL lower on POD 2 (830 vs. 1124 mL, P = 0.0002), and 305 mL lower on POD 3 (902 vs. 1205 mL, P = 0.0005) with a tendency for decreased transfusion rate (cases 17% vs. controls 26%) and total blood product consumption with no significant increase in the risk of thromboembolic event. This showing an 11% decrease in transfusion rates.(4, 12, 30)

In knee arthroplasty, study comparing routes of administration showed all routes had significant reduction of perioperative blood loss and transfusion needs with no superior route of administration.(4) (31)

Study comparing intravenous and topical TXA versus tourniquet showed intravenous TXA use without a tourniquet had less hidden blood loss, a lower ratio of postoperative knee swelling, less postoperative knee pain, lower levels of inflammatory biomarkers, better early knee function, and even better early satisfaction than those treated with a tourniquet.(32)

2.3.3 Tranexemic acid in femoral shaft fractures.

There is a paucity of literature on TXA use in femoral shaft fracture. Two literatures were addressing TXA use in femoral shaft fractures.

90 patient study in India looked at preoperative TXA 10mg/kg in femoral and hip surgeries, looked at postoperative drain volume ($39.33\pm$ as compared to $91.11\pm$ in placebo) 56.8% less than placebo, postoperative heamoglobin on days 0 (2.99 ± 3.457 in the study group as compared to 7.70 ± 6.05 in the placebo a 61.1% difference that has P value 0.01) and 2 (0.3578 ± 0.744 and in

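### Objective 2 claims a 30% cut in transfusion rates, but the single-arm plan adopts no untreated transfusion rate, so its named analysis cannot estimate a reduction

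*Combined protocol and SAP*

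**What the plan says.** Section 3.1 fixes the design: "This will be an open label single arm trial". No section of the protocol text describes a control group.

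Section 1.4 hypothesises that TXA "will reduce average perioperative blood loss of 3.31 g/dl and perioperative transfusion rates by 30" percent. Objective 2 in 3.12 repeats the 30% for transfusion. Section 1.6.2.2 states the same objective without a figure.

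The analysis given for Objective 2 is one sentence: "We will conduct univariate analysis and adjust for effect modification and confounding". The opening paragraph of 3.12 also offers "chi square or Fischer's test for categorical variables and a one sample independent T-test or wilcoxon sum rank test for continuous variables", without assigning any of these to transfusion.

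Section 3.8.2 defines the transfusion outcome as a count of blood units.

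Blood loss is treated differently. Section 3.6.1 takes a reference from the Mulago cohort, which "estimated 72 hours postoperative mean total blood loss at 3.31g/dl", and states that "Tranexemic Acid is expected to give 30% reduction in Blood Loss". Section 3.12 gives Objective 1 a one-sample t-test. Transfusion receives neither a reference value nor a named comparison.

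**The concern.** A reduction is a contrast between a treated rate and an untreated one. With one arm, the untreated rate must come from outside the trial, and the plan has to name it. Without it, an analyst who follows 3.12 will produce associations between baseline or surgical factors and transfusion among TXA-treated patients. That does not answer Objective 2.

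The practical risk lies in the report. Anyone who wants to say whether the 30% was achieved must choose a baseline that the plan does not contain, possibly with the results in hand. The choice can change the conclusion. Section 1.3 expects hospitals and the Ministry of Health to draw protocols and guidelines from the findings, so the transfusion claim may be used.

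**Working it through.** **1. What the plan's own calculation covers.** Inputs from 3.6.1: mean 3.31 g/dl, SD 1.56, 30% reduction, Z values 1.96 and 0.84.

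- Difference: 0.3 × 3.31 = 0.993 g/dl.
- n = (1.96 + 0.84)² × 2 × 1.56² / 0.993² = 7.84 × 4.8672 / 0.986 = 38.7, so 39.
- 39 / 0.9 = 43.3, stated as 43.

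The stated figures reproduce. Every input concerns blood loss, so the sample size carries no assumption about transfusion.

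**2. What the named analysis can estimate.** If every patient is treated, the treatment indicator is constant and its effect cannot be estimated, with or without adjustment. Chi-square or Fisher tests within one arm can compare only covariate subgroups, because no comparison group or reference proportion is given.

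**3. Scale of the 30%.** A relative reading is the most natural.

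- Section 1.4 uses one figure for blood loss and transfusion, and 3.6.1 works it as relative.
- Section 2.3.1 reports "33% reductions in blood transfusion" with the interval 0.54 to 0.83. The geometric midpoint is √(0.54 × 0.83) = 0.669, a 33% relative reduction.
- Thirty percentage points would be impossible from a 26% baseline and would require zero transfusions from 30%.

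The scale still has to be stated, because 2.3.3 describes transfusion effects as point differences: 18/45 − 7/45 = 24.4 points, and 30% − 5.6% = 24.4 points, each given there as 25%.

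**4. How much the baseline matters (illustration only).** Chapter 2 quotes three control rates: 26% (hip arthroplasty, 2.3.2), 30% (proximal femoral shaft nailing, 2.3.3) and 40% (mixed hip and femoral surgery, 2.3.3). The plan adopts none. The largest transfused count at which a 30% relative cut appears met is the whole-number part of 0.7 × p0 × n.

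| Assumed untreated rate p0 | n = 43 | n = 39 |
|---|---|---|
| 26% | 7.83 → 7 | 7.10 → 7 |
| 30% | 9.03 → 9 | 8.19 → 8 |
| 40% | 12.04 → 12 | 10.92 → 10 |

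For any count from 8 to 12 of 43, or 8 to 10 of 39, the target is met or missed according to the baseline chosen. With only the two studies in 2.3.3 (30% and 40%), the bands are 10 to 12 of 43 and 9 to 10 of 39.

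These thresholds concern the point estimate only. As an assumed example, 10 of 39 transfused is 25.6%, with an exact 95% CI of 13.0% to 42.1%. The implied relative reduction is 1.4%, 14.5% or 35.9% against 26%, 30% or 40%.

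**The case against.** **A comparison group may have been intended.** Section 3.6.1 defines n per group, the data sheet in Appendix II has a study-arm field with options A and B, and adjusting for confounding makes most sense when groups are compared. The Objective 2 sentence could be left over from a two-arm layout. This stands as a reason to ask the sponsor first. It does not close the gap, because the protocol text describes one arm and no source of controls. Nor do these fragments show that a control arm exists.

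**Control rates are in the document.** Chapter 2 does quote them, for example "decreased transfusion rate (cases 17% vs. controls 26" percent in hip arthroplasty. They are background from other settings or procedures, they differ from one another, and none is carried into the hypothesis, sample size or analysis.

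**The illustration rests on assumptions.** This is correct. The 26% comes from arthroplasty, and the bands narrow without it. The table shows only that the answer depends on the baseline. It does not predict a result or show that the trial would miss its target.

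**The endpoint definition is partly a matter of choice.** This is also correct. The mismatch between units and rates needs resolving, but the documents do not dictate the proportion transfused as the answer.

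**Stronger readings a reader might infer.**

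- One is that the primary objective falls too. Transfused units do enter the blood-loss formula in 3.7.8, but that analysis has its own reference value (3.31 g/dl) and needs no untreated transfusion rate.
- Another is that units given after 72 hours would contaminate the outcome, since follow-up lasts 2 weeks. The operational definitions end the perioperative period at 72 hours. On the data sheet, the units feed the perioperative formula beside the 72-hour haemoglobin, so the documents do not support that as a separate defect.

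**Conclusion.** The point holds for the secondary transfusion objective. Untreated transfusion rates adopted in the plan: none. Followed as written, 3.12 cannot estimate the reduction claimed in 1.4 and Objective 2, and it leaves the endpoint (units or rate) and the scale of the 30% unsettled. This conclusion rests only on the single-arm design and the absence of a reference rate. The counts of 7, 9 and 12 of 43 (7, 8 and 10 of 39) also assume the chapter 2 control rates and a relative 30%.

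The documents do not support saying that TXA will fail to reduce transfusion, or attaching one power figure to Objective 2, since there is no baseline from which to compute it. The matter should be settled before enrolment.

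**What to change.** 1. **Reconcile the design.** Confirm that the trial is single arm, and align the per-group formula in 3.6.1 and the study-arm field in Appendix II with 3.1.
2. **Define one endpoint that matches a rate.** For example, use the proportion of patients receiving at least 1 unit from start of surgery to 72 hours, with units per patient as a supporting summary (3.8.2).
3. **By default, make Objective 2 descriptive.** Report the proportion with an exact 95% CI, and delete the 30% figure for transfusion from 1.4 and from Objective 2 in 3.12.
4. **Claim a historical reduction only on one condition.** An untreated transfused count and denominator from the Mulago cohort must be obtained and written into the plan before enrolment. The documents do not show whether that count is available. If it is used, state that 30% is relative (target risk ratio 0.70). Report the risk ratio and risk difference with 95% CIs that include the sampling error of the historical group. Note that any difference may also reflect the transfusion guideline supplied to the teams (3.7.6, Appendix III).
5. **In either case, relabel the covariate models** as exploratory predictors of transfusion among TXA-treated patients.

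The cost is wording in 1.4, 3.6.1, 3.8.2, 3.12 and the data sheet, plus one historical count if that route is taken. No extra patients or arm are needed. The downside is that the transfusion claim becomes descriptive or historical.

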the placebo was 2.7122 ± 2.70 , P value 0.000) a difference of 86.6% Results showed preoperative TXA caused a highly significant reduction in the blood loss in the first 24 hours in patients undergoing surgeries for hip and femoral fractures as well it caused a significant reduction in postoperative anemia and need for transfusion among these patients. In this study out of 45 patients, 18 patients (40%) who fell in the placebo group required blood transfusion and while 7 patients out of 45 (15%) in the study group needed a transfusion ($P=0.01$) a 25% difference in transfusion rates. This study recommended further investigation to determine the effectiveness of TXA in these surgeries.(33)

In Iran, double blinded randomized controlled clinical trial on role of preoperative TXA 15mg/kg versus placebo in intramedullary nailing of proximal femoral fracture shaft was done. With total of 40 patients, each study group was allocated 20 patients. Hemoglobin concentration was used to estimate blood loss, hemoglobin level was measured four hours before and after the surgeries. Blood transfusions observed and integrated into the blood estimation formula. Results showed No significant difference was observed between the groups in drain blood volume four hours after surgery. Mean fall in hemoglobin concentration in placebo group was higher than the TXA group, however, the difference was not statistically significant. ($P= 0.570$) A difference in transfusion rate between the placebo group (30%) and TXA group (5.6%) was also not statistically significant ($P=0.06$) a difference of 25%. Surgeon satisfaction level was also observed and noted to higher in the TXA group (94.4%) compared to the placebo group (80%), however the difference was not statistically significant. The study concluded that intravenous TXA before skin incision in patient undergoing proximal femoral shaft fractures surgery, may reduce intraoperative blood loss and hemoglobin fall however without significant reduction in postoperative anemia. This study recommended further investigations.(34)

CHAPTER THREE

METHODOLOGY

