3.8 Study variables

3.8.1 Independent Variables

Demographics

- . Age
- . Sex
- . Weight

Clinical

- . Pre-operative Hemoglobin

Fracture

- . Duration of Injury
- . Fracture Pattern (AO / OTA)

Surgery

- . General Anaesthesia
- . Regional Anaesthesia
- . Antegrade Nailing Technique

- . Retrograde Nailing Technique
- . Duration of Surgery

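### Objective 2 plans to adjust transfusion for effect modification and confounding, but in a single-arm trial covariate associations are prognostic and cannot describe the effect of tranexamic acid

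*Combined protocol and SAP*

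**What the plan says.** Section 3.1 fixes the design: "This will be an open label single arm trial involving adult patients". Section 1.6.2.2 makes the effect of tranexamic acid on transfusion rates a secondary effectiveness objective, and 1.4 and 3.12 attach a 30% reduction to it.

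The analysis of that objective in 3.12 is one sentence: "We will conduct univariate analysis and adjust for effect modification and confounding". It names no model, covariates, alpha or multiplicity rule, and it does not call the work exploratory. The only multiplicity provision is the Bonferroni statement in 3.10.2, which concerns the interim efficacy analysis.

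The only list of candidate variables is under "3.8.1 Independent Variables". It has eleven bullets: age, sex, weight, pre-operative haemoglobin, duration of injury, "Fracture Pattern (AO / OTA"), general and regional anaesthesia, antegrade and retrograde nailing, and duration of surgery. Objective 2 does not refer to that list. Section 3.8.2 defines the transfusion outcome as a number of units, whereas the objective speaks of rates.

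**The concern.** Effect modification means that the effect of treatment differs across levels of a covariate. Confounding of a treatment effect means that treated and untreated patients differ in something that also affects the outcome. Both need treatment to vary, and here it does not. What can be estimated is which treated patients are more likely to be transfused.

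The sentence sits under an effectiveness objective and uses the vocabulary of treatment effects. A prognostic association, for example between pre-operative haemoglobin and transfusion, could therefore be reported as a difference in how well the drug works, or an adjusted coefficient as an adjusted drug effect. Section 1.3 expects hospitals and the Ministry of Health to use the findings for protocols and guidelines, so such a misreading would have consequences. The likely small number of transfusions adds two problems: chance associations, and a multivariable model with too little information behind it.

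**Working it through.** **What a single arm identifies.** Write P(transfusion | treatment, covariate). Effect modification compares the treated-minus-untreated contrast at different covariate values. With every patient treated, only the treated term is observed at each value. A difference between those terms could come from a differing drug effect, from differing background risk, or from both, and the data cannot separate them. An external overall transfusion rate would not change this; untreated rates at each covariate level would be needed.

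**Sample size, reproduced.** Inputs from 3.6.1 are "1.96 for 95% confidence level", "0.84 for 80% power", "mean total blood loss at 3.31g/dl, (SD 1.56") and a 30% reduction, 0.3 × 3.31 = 0.993.
- n = (1.96 + 0.84)² × 2 × 1.56² / 0.993² = 38.7, so 39.
- 39 / 0.9 = 43.3, which the plan gives as 43.

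This sizes the blood-loss endpoint. The documents give no expected number of transfusions and no error rate for Objective 2, so the rest is illustration.

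**Number of factors (inferred).** Eleven bullets become nine when the anaesthesia pair and the nailing pair each count once. Fracture pattern has three levels on the data sheet (A, B, C), so a model with all nine factors has 8 + 2 = 10 parameters.

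**False positives (5% level assumed from the sample-size formula).**
- Nine independent tests at exactly 5%: 1 − 0.95⁹ = 37.0%.
- Simulated equicorrelated normal tests: about 33% at correlation 0.3 and 27% at 0.5. These correlations are assumptions.
- With few events, discrete tests do not run at 5%. I took five rank-sum tests and four two-group tests (9, 17, 17 and 20 of 43 in one group, fracture pattern dichotomised), treated as independent, with exact null sizes.
  - With 2–7 events, Fisher tests give 21–31% and uncorrected chi-square 23–40%.
  - Low end, 3 events, Fisher: 1 − (1 − 0.0444)⁵ × (1 − 0.0068) = 20.9%, since the other three Fisher tests can never reach 0.05.
  - High end, 5 events, chi-square: 1 − (1 − 0.0488)⁵ × (1 − 0.054)(1 − 0.071)²(1 − 0.051) = about 39.6%.
  - At 9–12 events the same formula stays inside that span. For example, 9 events, Fisher: 1 − (1 − 0.0493)⁵ × (1 − 0.011)(1 − 0.018)²(1 − 0.024) = 27.7%.

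A fair summary is about 20–40%. Correlation and discreteness acting together could take it lower; added interaction tests would take it higher.

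**Events per parameter (43 patients, 10 parameters).** The rates come from the two femoral-fracture studies in 2.3.3. One reports 5.6% transfused on tranexamic acid and 30% on placebo. In the other, "7 patients out of 45 (15%) in the study group needed a transfusion", against 40% on placebo.

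| Assumed rate | Events of 43 | Per parameter |
|---|---|---|
| 5.6% (treated arm) | 2.4 | 0.24 |
| 15% (treated arm) | 6.5 | 0.65 |
| 0.7 × 30% = 21% | 9.0 | 0.90 |
| 0.7 × 40% = 28% | 12.0 | 1.20 |

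The last two rows apply the trial's own 30% reduction to the cited placebo rates. Across the whole range there is about one event per parameter or fewer.

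**The case against.** The best defence is that the sentence is loose rather than wrong. Adjusting for covariates normally treats them as nuisance factors and does not commit anyone to reporting each association as a finding. Confounding might mean case-mix differences from the earlier Mulago cohort used in 3.6.1. Part of this stands: the text does not say that every association will be claimed. But adjusting against a historical cohort needs that cohort's covariate data and a reference transfusion rate, and the plan provides neither. No such reading rescues effect modification. The data sheet in Appendix II still has a field for arm A or B, and the sentence would make sense in a two-arm trial, but the abstract and 3.1 describe one arm.

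Three criticisms of the numbers also stand. The nine factors and the 5% level are inferred, because Objective 2 states neither. The events come from outside studies: taking only their treated arms gives 2–7, while the trial's own hypothesis gives 9–12, so neither range alone describes this trial. And events per parameter presupposes a yes/no outcome, whereas 3.8.2 counts units.

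A reader might infer that the plan commits to nine tests at full alpha and would probably report a chance subgroup effect. The documents do not support that. An illustrative 20–40% is below one half, the tests counted are main-effect associations rather than interactions, and the plan sets no test family.

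**Conclusion.** Wrong as written. The stated analysis of Objective 2 names quantities that this design cannot estimate, and following it could present prognostic associations as properties of the drug. This conclusion rests only on 3.1 and 3.12 and needs no numerical assumption.

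The numbers show why the covariate work should also be labelled exploratory and kept small. They depend on merging the 3.8.1 list to nine factors, an assumed 5% level, and transfusion rates borrowed from two cited studies. The point concerns a secondary objective and leaves the one-sample test of blood loss untouched. It is also separate from the missing reference transfusion rate, and would remain if one were supplied.

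**What to change.** In 3.12, Objective 2, keep an analysis of the objective itself and replace the adjustment clause. Suggested text:

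*The proportion of patients transfused will be reported with an exact 95% CI, together with the number of units, as the Objective 2 estimate. Associations between the variables in 3.8.1 and transfusion are exploratory and prognostic, reported as estimates with 95% CIs without significance claims; no effect modification of tranexamic acid is inferred, and no model with all the listed covariates is fitted.*

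The first sentence is needed because the present sentence is the only analysis Objective 2 has; prognostic wording alone would leave the objective without one. It does not supply the missing reference rate for the 30% reduction, which must be settled separately.

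The cost is a short edit and less analysis work. What is given up is multi-covariate adjusted results, which about 43 patients cannot support.
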